### **2.5.2. Decitabine**

Decitabine was studied in 3 single-arm studies (N=66, N=98, N=99) and 1 controlled supportive care study (N=83 decitabine, N=81 supportive care). The data described below reflect exposure to decitabine in 83 patients in the MDS trial. In the trial, patients received 15 mg/m^2 intravenously every 8 hours for 3 days every 6 weeks. The median number of decitabine cycles was 3 (range 0 to 9).

*Most Commonly Occurring Adverse Reactions:* neutropenia, thrombocytopenia, anemia, fatigue, pyrexia, nausea, cough, petechiae, constipation, diarrhea, and hyperglycemia.

*Adverse Reactions Most Frequently ( $\geq 1\%$ ) Resulting in Clinical Intervention in the Phase 3 Trials in the decitabine Arm:*

Discontinuation: thrombocytopenia, neutropenia, pneumonia, Mycobacterium avium complex infection, cardio-respiratory arrest, increased blood bilirubin, intracranial hemorrhage, abnormal liver function tests.

Dose Delayed: neutropenia, pulmonary edema, atrial fibrillation, central line infection, febrile neutropenia.

Dose Reduced: neutropenia, thrombocytopenia, anemia, lethargy, edema, tachycardia, depression, pharyngitis.

In the controlled trial using decitabine dosed at 15 mg/m^2, administered by continuous intravenous infusion over 3 hours repeated every 8 hours for 3 days, the highest incidence of Grade 3 or Grade 4 adverse events in the decitabine arm were neutropenia (87%), thrombocytopenia (85%), febrile neutropenia (23%) and leukopenia (22%). Bone marrow suppression was the most frequent cause of dose reduction, delay and discontinuation. Six patients had fatal events associated with their underlying disease and myelosuppression (anemia, neutropenia, and thrombocytopenia) that were considered at least possibly related to drug treatment. Of the 83 decitabine-treated patients, 8 permanently discontinued therapy for adverse events; compared to 1 of 81 patients in the supportive care arm.

In a single-arm phase 1 study of patients with hematological malignancies (N=48) decitabine was dosed at 5, 10, 15 or 20mg/m^2 daily intravenously over one hour for 10 days (5 days on, 2 days off, 5 days on), approximately every six weeks. 73% of these patients had AML and 14% had MDS. The treatment was well tolerated overall. Nonhematopoietic side effects are detailed in Table 2 below. Asymptomatic but severe

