### **4.0 ELIGIBILITY ASSESSMENT AND ENROLLMENT**

#### **4.1. Inclusion Criteria**

- Unequivocal diagnosis of relapsed or refractory acute myeloid leukemia (AML) confirmed by an NIH attending pathologist within 30 days of study enrollment (includes residual AML as confirmed by institutional standards by NIH pathologists, see Appendix A).
- Received at least one prior AML therapy-before study enrollment.
- Ability to comprehend the investigational nature of the study and provide informed consent.
- Be at least 18 years of age on day of signing informed consent.
- Availability of a physician willing to assume clinical care after completion of the study.
- Be willing to provide blood and bone marrow for research as described in the study.

- Have a performance status of less than or equal to 1 on the ECOG Performance Scale (Appendix B).
- Demonstrate adequate organ function as defined in Table 3, all screening labs should be performed within 14 days of treatment initiation.
- Female subject of childbearing potential should have a negative urine or serum pregnancy within 72 hours prior to receiving the first dose of study medication. If the urine test is positive or cannot be confirmed as negative, a serum pregnancy test will be required.
- Female subjects of childbearing potential (Section 5.7.2) must be willing to use an adequate method of contraception as outlined in Section 5.7.2 – Contraception, for the course of the study through 120 days after the last dose of study medication. Note: Abstinence is acceptable if this is the usual lifestyle and preferred contraception for the subject.
- Male subjects of childbearing potential (Section 5.7.1) must agree to use an adequate method of contraception as outlined in Section 5.7.1- Contraception, starting with the first dose of study therapy through 120 days after the last dose of study therapy. Note: Abstinence is acceptable if this is the usual lifestyle and preferred contraception for the subject.

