## 5.2. Dose Modification Guidelines For Drug-Related Adverse Events

### 5.2.1. Hematologic toxicities

Given the pathobiology of Acute Myeloid Leukemia, severe blood count abnormalities (up to grade 4 levels in leukocytes, neutrophils, lymphocytes, red blood cells and platelets) are expected and may be present at baseline.

Decitabine will be initiated on Cycle 1 and 3 regardless of peripheral blood count values. After this point, if hematologic recovery (absolute neutrophil count  $\geq 1,000/\mu\text{L}$  and platelets  $\geq 50,000/\mu\text{L}$ ) does not occur six weeks after initiation of prior cycle of decitabine in complete remission patients, then subsequent decitabine doses will be modified to consist of five days of 20mg/m^2 given, at the discretion of the investigator, anytime during days 8-19 of a cycle.

In accordance with the FDA label and past clinical trial experience no dose modification will be made for pembrolizumab in the event of hematological toxicity.

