**Table 7: Clinical Endpoints**

Outcome	Included Patients	Point of Measurement	Definition
Feasibility	All	Interim Analysis/Safety Follow-Up Visit (see Section 6.5.1)	Descriptive summary of all adverse events (number, severity and duration of adverse events) according to NCI-Common Terminology Criteria for Adverse Events (CTCAE) v4.0
Efficacy	All	Following cycles 2, 4, 6, 8 and at progression/off-study time-point	Descriptive summary of conventional response criteria as described in Appendix A. In addition any clinical information regarding MRD status (eg: flow cytometry, cytogenetics, PCR) will be captured at these time-points.
Time to first response	Responders (mCR, mCRi,, CR, CRi, PR)	As above	Defined as time from start of study to initial achievement of first response.
Time to best response	As above	As above	Defined as time from start of study to initial achievement of best response.
Duration of response	As above	As above	Defined as time from initial achievement of response to loss of response.
Duration of best response	As above	As above	Defined as time from initial achievement of best response to loss of best response.
Overall survival	All	Entry onto trial	Death from any cause

**Bone marrow examinations for clinical response assessment will be performed pre-treatment and after cycles 2, 4, 6 and 8 (or the progression/off-study time-point).** Bone marrows after cycles 2, 4, 6 and 8 may be performed anytime in the week prior to the next cycle of Pembrolizumab (*ie:* the “after cycle 2” marrow may be performed prior to the pembrolizumab dose on day 1 of cycle 3 or anytime in the preceding week). Assessments will include clinical pathological assessment by morphology, flow cytometry and cytogenetics. An additional bone marrow for research purposes may be performed on or around day 8 of cycle 1. Additional bone marrows may be done after cycle 8, until progression as clinically indicated.

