### 9.1.2. Severity

The descriptions and grading scales found in the revised NCI Common Terminology Criteria for Adverse Events (CTCAE) version 4.03 will be utilized for grading the *severity* (intensity) of **non-hematologic** AEs (<http://ctep.cancer.gov/reporting/ctc.html>).

Given the pathobiology of Acute Myeloid Leukemia, severe blood count abnormalities (up to grade 4 levels in leukocytes, neutrophils, lymphocytes, red blood cells and platelets) are expected and may be present at baseline. Thus we will record these values in the protocol database, but will not report these abnormalities as adverse or serious adverse events unless the grade of toxicity (based on NCI-Common Terminology Criteria for Adverse Events, CTCAE v4.0) is grade 4 or above and was not present at baseline. If the myelosuppressive event is fatal (Grade 5), or if the Investigator finds the event to be medically important, then it will be collected as an SAE.

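### New cytopenias below grade 4, and non-recoveries that shorten decitabine, need not appear in the primary feasibility summary

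*Combined protocol and SAP*

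**What the plan says.** Section 9.1.2 reasons that severe count abnormalities are expected in AML and may be present at entry. It keeps the data: "Thus we will record these values in the protocol database". It then says the trial "will not report these abnormalities as adverse or serious adverse events unless the grade of toxicity" "is grade 4 or above and was not present at baseline". Both conditions must hold, and they are the same for every patient. The next sentence adds an exception for fatal events and a discretionary one: "if the Investigator finds the event to be medically important, then it will be collected as an SAE".

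Table 7 (Section 6.3) defines the feasibility outcome, which is the primary objective, as: "Descriptive summary of all adverse events (number, severity and duration of adverse events".

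The eligible population "includes residual AML as confirmed by institutional standards by NIH pathologists" (Section 4.1). Appendix A foresees entry already in CR or CRi with residual disease only. CR requires ANC of at least 1,000/mcl and platelets of at least 100,000/mcl.

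Section 5.2.1 starts decitabine in cycles 1 and 3 whatever the counts. After that, if a complete remission patient has not recovered to ANC 1,000/µL and platelets 50,000/µL six weeks after the previous decitabine course began, "then subsequent decitabine doses will be modified to consist of five days".

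**The concern.** The trial asks whether pembrolizumab can be given safely with decitabine, and marrow suppression is decitabine's dominant known toxicity. Section 2.5.2 reports grade 3 or 4 neutropenia in 87% and thrombocytopenia in 85% of decitabine patients in the controlled MDS trial, and names marrow suppression as the most frequent cause of dose reduction, delay and discontinuation.

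The reason given in 9.1.2, that the leukemia itself lowers the counts, fits poorly for a patient who enters in morphologic CR. In a single-arm trial, a new cytopenia in such a patient is among the clearest marrow-toxicity signals available. If it peaks at grade 3, the plan does not require it to become an adverse event. Nor does anything in 5.2.1 or 9.1.2 make a count-driven change of decitabine an adverse event. A reader of the primary summary could then see a cleaner hematologic profile than the database holds, and could miss that treatment had to be changed.

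**Working it through.** The plan states no figure on this point, so the check sets the provisions side by side.

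**Routes by which a new, non-fatal cytopenia below grade 4 can reach the Table 7 summary**

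- *Grade rule, 9.1.2:* no, because grade 4 or above is required.
- *Medically important, 9.1.2:* yes, with no minimum grade, but at the investigator's discretion and without criteria.
- *Event of clinical interest, 9.6 with Appendix C:* these go on the adverse event forms. Listed hematologic events, such as autoimmune hemolytic anemia, aplastic anemia and immune thrombocytopenia, count at grade 3 or above, or at any grade leading to dose modification. Any other grade 3 event that the physician considers immune-related also counts. Plain neutropenia and thrombocytopenia are not listed.
- *Stopping rule, 8.3:* no, because its endpoint excludes hematological toxicity.
- *5.2.1 modification:* no link to adverse event reporting is stated.

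A new grade 3 neutropenia or thrombocytopenia attributed to decitabine, and not judged medically important, therefore has no required route into the primary summary.

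**Is the gap realistic?** CTCAE cut-offs are not in the documents. Assume grade 4 means platelets below 25 x 10^9/L and ANC below 0.5 x 10^9/L. Section 2.5.2 gives nadirs for 10 decitabine courses in 6 remission patients, 8 of them at 15 mg/m² for 10 days:

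- *Platelets:* median nadir 45 (range 20 to 200). Since 25 < 45 < 50, the median nadir is below the 5.2.1 recovery level but not grade 4.
- *Granulocytes:* median nadir 0.32 (range 0 to 3.0). Since 0.32 < 0.5, the median nadir is grade 4, and if new it is reported under 9.1.2.

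The gap is thus firmer for platelets than for neutrophils.

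**Can 5.2.1 be triggered without an adverse event?** The trigger is failure to reach both recovery levels at six weeks (42 days), in complete remission patients, after the cycle 3 course. Under the assumed cut-offs, a patient whose counts never went below ANC 500 or platelets 25,000, but who is still below 1,000 or 50,000 at that check, meets 5.2.1 and not the 9.1.2 grade rule. A patient whose counts newly reached grade 4 earlier has that nadir reported, though still not the modification itself.

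**Size.** Let q be the per-patient chance of such an unreported event. The documents do not give q, so these values are pure assumption. With 10 patients, the chance of at least one is 1 − (1 − q)^10:

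- q = 0.05: 1 − 0.599 = 40%
- q = 0.10: 1 − 0.349 = 65%
- q = 0.20: 1 − 0.107 = 89%
- q = 0.30: 1 − 0.028 = 97%
- q = 0.50: 1 − 0.001 = over 99%

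This shows only that even a modest rate would probably touch someone in a trial of this size. It does not estimate how many.

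**The case against.** The strongest reply is that nothing is lost. Values go to the database (9.1.2), hematology is part of the safety assessment (9.1), and Appendix G keeps a treatment administration log through cycles 1 to 8. Where to set the adverse event threshold for cytopenias in AML is a matter of convention, and a high threshold avoids filling the listing with disease effects. That stands: this is a gap in the summary, not in data capture, and it is no reason to move the threshold.

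Several stronger readings are tempting, and the documents do not support them:

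- *Every new cytopenia below grade 4 is kept out.* The medically important route and the events of clinical interest contradict this.
- *Grade 3 immune thrombocytopenia is lost.* Appendix C lists it at grade 3 or above and 9.6 puts it on the adverse event forms. Section 9.6 also presumes an immune cause where no other is found. With decitabine on board, however, another cause is usually at hand for a plain cytopenia.
- *Residual-disease patients enter with normal counts.* CR sets floors for ANC and platelets only, with no hemoglobin requirement, and CRi allows lower counts.
- *Any count in the grade 3 band triggers 5.2.1.* The trigger is confined to complete remission patients at six weeks, after cycle 3.
- *The 87% and 85% rates give a number of affected patients.* They come from an MDS trial on another schedule, do not separate grade 3 from grade 4, and do not say what was new since baseline.

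It could also be argued that not reporting an abnormality as an adverse event does not bar it from a summary. True, but Table 7 summarizes adverse events and nothing tells the analyst to add count data.

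**Conclusion.** The point holds in limited form. The plan does not require new sub-grade-4 neutropenia or thrombocytopenia, or a 5.2.1 non-recovery, to appear in the primary feasibility summary, and the stopping rule is no backstop. The reporting gap follows from the text alone.

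That it is realistic for platelets rests on the assumed grade 4 cut-off of 25 x 10^9/L and on 10 courses in 6 patients, mostly at a lower daily dose than this trial's 20 mg/m². For neutrophils the same source suggests that grade 4, and hence reporting, is more usual. The number of patients affected cannot be derived, and the documents do not say how many entrants, if any, had residual disease only. The trial's conduct is not called into question; the primary summary would simply be incomplete on the toxicity that matters most for decitabine.

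**What to change.** Leave the 9.1.2 threshold as it is. Section 11.3 says accrual closed on November 30, 2017 and that the study is in data analysis only from March 15, 2019, so changing the threshold now would mean retrospective coding and attribution. Instead, add two items to the Table 7 feasibility summary:

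1. A table of baseline grade against worst on-treatment grade for ANC, platelets and hemoglobin, from the values 9.1.2 already records. Mark each patient as residual-disease-only or overt leukemia at entry; with about ten patients, a marker per patient serves better than separate strata.
2. A list of every decitabine modification made under 5.2.1, taken from the treatment administration log.

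State how often counts were taken. Section 6.2 schedules them before each three-week cycle, so the worst recorded value may miss the true nadir unless interim results, including those from home physicians (10.6), are used.

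The cost is a little more analysis work and a less favourable-looking hematologic profile. No clinical rule changes and no new data are needed.

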### 9.1.3. Pregnancy

A patient will be advised to immediately inform the investigator if the patient or patient's partner becomes pregnant from the time of consent to 120 days of completing the trial, or 30 days following cessation of treatment if the subject initiates new anticancer therapy, whichever is earlier. If a subject inadvertently becomes pregnant while on treatment with the study regimen, the subject will immediately be removed from the study. The site will contact the subject at least monthly and document the subject's status until the pregnancy has been completed or terminated.

Although pregnancy and lactation are not considered AEs, it is the responsibility of investigators or their designees to report any pregnancy or lactation in a subject (spontaneously reported to them), including the pregnancy of a male subject's female partner that occurs during the trial. Abortion, whether therapeutic, elective or spontaneous, will be reported as an SAE, which includes pregnancy outcomes of spontaneous abortion, missed abortion, benign hydatidiform mole, blighted ovum, fetal death, intrauterine death, miscarriage and stillbirth. If the pregnancy continues to term, the outcome (health of infant) must also be reported.

The outcome of the pregnancy will be reported to Merck without delay and within 24 hours to the sponsor and within 2 working days to Merck if the outcome is a serious adverse experience (e.g., death, abortion, congenital anomaly, or other disabling or life-threatening complication to the mother or newborn). Such events must be reported to Merck Global Safety. (Attn: Worldwide Product Safety; [contact]).

### 9.1.4. Causality assessments

The following general guideline will be followed:

**Table 10: Causality Assessment Guideline**

Unrelated	Another cause of the AE is more plausible; a temporal sequence cannot be established with the onset of the AE and administration of the investigational product; or, a causal relationship is considered biologically implausible.
Unlikely to be Related:	A temporal sequence with the onset of the adverse event and administration of the investigational product is improbable, but not impossible. Concurrent or underlying disease, or the use of other drugs or procedures provide plausible explanations for the adverse event.
Possibly Related	There is a clinically plausible time sequence between onset of the AE and administration of the investigational product, but the adverse event could also be attributed to concurrent or underlying disease, or the use of other drugs or procedures. Possibly related should be used when the investigational product is one of several biologically plausible adverse event causes.
Probably Related:	There is a clinically plausible time sequence between onset of the adverse event and administration of the investigational product, and the adverse event is unlikely to be attributed to concurrent or underlying disease, or the use of other drugs or procedures. Clinical response to withdrawal of the investigational product may indicate the adverse event is probably related. Rechallenge with the investigational drug is not required.
Definitely Related	The AE is clearly related to use of the investigational product.

## 9.2. Documentation

Investigators will assess the occurrence of AEs and SAEs at all patient evaluation time points during the study. There are ten scheduled patient evaluation time-points; at baseline, after cycles 1-8 and at the safety follow-up visit (see also Appendix G). In addition, all AEs and SAEs whether volunteered by the patient, discovered by study personnel during questioning, or detected through physical examination, clinically significant laboratory test, or other means will be recorded in the patient's medical record.

### 9.3. NIH-IRB and Clinical Director Reporting

#### **Expedited Reporting**

Events requiring expedited reporting will be submitted to the IRB per Policy 801 “Reporting Research Events”.

#### **Reports to the IRB at the time of Continuing Review:**

The PI or designee will refer to HRPP Policy 801 “Reporting Research Events” to determine IRB reporting requirements.

#### **Reports to the CD:**

The PI or designee will refer to NHLBI DIR guidelines to determine CD reporting requirements and timelines.

### 9.4. Company Reporting

#### **Reports to Merck:**

A SAE is any AE occurring at any dose or during any use of Merck’s product that:

- Results in death;
- Is life threatening;
- Results in persistent or significant disability/incapacity;
- Results in or prolongs an existing inpatient hospitalization;
- Is a congenital anomaly/birth defect;
- Is a new cancer (that is not a condition of the study);
- Is associated with an overdose;
- Is an other important medical event

Any SAE, or follow up to a SAE, including death due to any cause other than progression of the cancer under study that occurs to any subject from the time the consent is signed through 90 days following cessation of treatment, or the initiation of new anti-cancer therapy, whichever is earlier, whether or not related to Merck product, must be reported within 24 hours to the sponsor and within 2 working days to Merck Global Safety.

Additionally, any SAE, considered by an investigator who is a qualified physician to be related to Merck product that is brought to the attention of the investigator at any time outside of the time period specified in the previous paragraph also must be reported immediately to the Sponsor and to Merck.

**SAE reports and any other relevant safety information are to be forwarded to the Merck Global Safety [contact]**

A copy of all 15 Day Reports and Annual Progress Reports is submitted as required by FDA, European Union (EU), Pharmaceutical and Medical Devices agency (PMDA) or other local regulators. Investigators will cross-reference this submission according to local regulations to the Merck Investigational Compound Number (IND, CSA, etc.) at the time of submission. Additionally investigators will submit a copy of these reports to Merck & Co., Inc. (Attn: Worldwide Product Safety; [contact]) at the time of submission to FDA.

All subjects with serious adverse events must be followed up for outcome.

Non-serious Events of Clinical Interest will be forwarded to Merck Global Safety and will be handled in the same manner as SAEs.

## 9.5. FDA Reporting Criteria

### 9.5.1. IND Safety Reports to the FDA (Refer to 21 CFR 312.32)

The Sponsor will notify the FDA of any unexpected fatal or life-threatening suspected adverse reactions as soon as possible but no later than 7 calendar days of initial receipt of the information using the MedWatch Form 3500a or other permitted method.

The Sponsor is also responsible for reporting any:

- suspected adverse reaction that is both serious and unexpected
- any findings from clinical, epidemiological, or pooled analysis of multiple studies or any findings from animal or in vitro testing that suggest a significant risk in humans exposed to the drug
- clinically important increase in the rate of a serious suspected adverse reaction over that listed in the protocol or investigator brochure to the FDA and to all investigators no later than 15 calendar days after determining that the information qualifies for reporting using the MedWatch Form 3500a. If FDA requests any additional data or information, the sponsor must submit it to the FDA as soon as possible, but no later than 15 calendar days after receiving the request.

